#### Sample Size

To detect a minimum standard effect size of 0.3 with 80% power and a two-sided 5% significance level would require 352 patients (176 in each group). Although this is an individually-randomised trial, there may be potential clustering at the level of each collaborative care case manager and hence the sample size was inflated to account for this. Based upon an ICC = 0.02 and a caseload size of 20, the design effect would be 1.38 ( $1 + (20 - 1) \times 0.02$ ) and 486 patients (243 in each group) would be required.

The original trial sample size allowed for 10% loss to follow-up, resulting in a total of 540 patients (270 in each group). Following the inspection of interim recruitment figures and disproportionate dropout from the collaborative care arm, this assumption was revised (Substantial Amendment 17). Allowing for a loss to follow-up of 26%, the final sample size needed is 658 patients (329 in each group).

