### **Other Collected Data**

- Demographic details at invitation
- Whooley Questions at invitation and baseline
- Questions about physical health problems at baseline
- Questions about falls at baseline
- PHQ-9 at diagnostic interview
- M.I.N.I. (Major depressive episode module) at diagnostic interview
- PHQ-15 at baseline, 4 & 12 months
- CD-RISC 2 at baseline, 4 & 12 months
- Adverse events (as arising up to 12 months follow-up)
- Economic Evaluation at baseline, 4 & 12 months

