## **Analysis Population**

The analysis population will include all patients in their randomised groups with available outcome data (for the primary analysis: PHQ-9 at 4 months or 12 months follow-up) as well as complete baseline covariates specified for the analysis.

Data from withdrawn participants were retained up to the date of withdrawal, unless they specifically requested for their details to be removed. Where withdrawal was only from the intervention, follow-up data were continued to be collected. If participants were lost to follow-up due to death or migration, their data were included in the main analysis up to where they have been lost to follow-up.

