### **Adverse Events**

Frequencies of any reported adverse events will be summarised by trial arm and overall. Figures will include a breakdown by type of event and relatedness to the intervention. The details of adverse events will be categorised and reported descriptively. The number and percent of patients experiencing at least one adverse event as well as the average number of adverse events per patient will be presented.

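### Adverse events are summarised per patient with no account of time observed, although the SAP reports unequal dropout; the figures may understate non-fatal events in collaborative care

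*SAP*

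**What the plan says.** **The summary.** Section 6, Adverse Events, is descriptive: "Frequencies of any reported adverse events will be summarised by trial arm and overall", broken down by type of event and relatedness. It continues: "The number and percent of patients experiencing at least one adverse event as well as the average number of adverse events per patient will be" reported. It gives no person-time, no incidence rate and no rule for patients whose observation ends early. It does not name its denominator; section 6, Principles, implies everyone randomised, in the arm allocated.

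**The window.** Section 4, Other Collected Data, lists "Adverse events (as arising up to 12 months follow-up"), the same nominal period in both arms.

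**Retention.** Section 3, Sample Size, first allowed for 10% loss. Then: "Following the inspection of interim recruitment figures and disproportionate dropout from the collaborative care arm, this assumption was revised". The new allowance is 26%, with no split by arm and no statement of the kind of dropout.

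**Withdrawal.** Section 6, Analysis Population, states: "Data from withdrawn participants were retained up to the date of withdrawal". It adds that people who left only the intervention stayed in follow-up.

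**Capture of events.** Section 4 has deaths found by NHS flagging of every randomised participant, and serious events picked up continuously and entered on a dedicated form. Section 5, Data Sources, takes adverse event details from local investigator spreadsheets, separate from the questionnaires.

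**The concern.** A per-patient percentage or mean compares the arms fairly only if patients in each arm were observed for about the same time. A participant who withdraws fully at month 2 can contribute two months of events but counts as one whole patient in the denominator. If more participants leave one arm in this way, that arm shows fewer events per patient even when the true rates are equal.

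The SAP itself reports unequal retention, so the condition that makes these summaries fragile was known when they were specified. Apart from the mortality test, the crude figures are the whole safety comparison, and a reader could take a lower percentage in collaborative care as evidence about harm when part of it reflects shorter observation. The dropout frequencies by arm promised in Trial Progression would not let that reader recover a rate, because frequencies alone do not give person-time.

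**Working it through.** **1. The SAP's own figures.** The Adverse Events section gives no number; the only quantified dropout input is in Sample Size.

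- Effect size 0.3, 80% power, two-sided 5%: 2 × (1.96 + 0.84)² / 0.3² gives 175 per arm, 350 in total, by the normal approximation. The SAP has 352, which agrees within the approximation.
- Design effect: 1 + 19 × 0.02 = 1.38, and 352 × 1.38 = 485.8, so 486 as stated.
- 10% loss: 486 / 0.90 = 540 as stated.
- 26% loss: 243 / 0.74 = 328.4, rounded up to 329 per arm, 658 in total as stated.

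The 26% is therefore used as a single overall figure, equal in both arms, although the text says dropout was unequal.

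**2. Effect of unequal observation.** Assumptions, none of them SAP figures: the same constant event rate r per person-year in both arms; a proportion d of the arm drops out, all at fraction f of the year; nothing is recorded after dropout. Splits are chosen to average 26%, for example (36 + 16) / 2.

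Mean events per patient = r × [(1 − d) + d × f].

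The rate r cancels in the ratio of collaborative care (CC) to usual care (UC):

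| Loss CC / UC | Dropout at month 0 | Month 4 | Month 6 |
|---|---|---|---|
| 26% / 26% | 1.00 | 1.00 | 1.00 |
| 31% / 21% | 0.690 / 0.790 = 0.87 | 0.793 / 0.860 = 0.92 | 0.845 / 0.895 = 0.94 |
| 36% / 16% | 0.640 / 0.840 = 0.76 | 0.760 / 0.893 = 0.85 | 0.820 / 0.920 = 0.89 |
| 42% / 10% | 0.580 / 0.900 = 0.64 | 0.720 / 0.933 = 0.77 | 0.790 / 0.950 = 0.83 |

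Over the unequal splits the ratio runs from 0.64 to 0.94, with a true ratio of 1.0. Events per person-year would return 1.0 in every cell.

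**3. Percent with at least one event.** Percent = (1 − d)(1 − e^(−r)) + d(1 − e^(−r × f)). With r = 0.2 (assumed) and the 36% / 16% split:

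- Dropout at month 0: 0.64 × 0.1813 = 11.6% in CC, and 0.84 × 0.1813 = 15.2% in UC.
- Dropout at month 6: 0.64 × 0.1813 + 0.36 × 0.0952 = 15.0% in CC, and 0.84 × 0.1813 + 0.16 × 0.0952 = 16.7% in UC.

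**4. When the effect vanishes or is cancelled.** If events are still recorded after dropout, observed time is the same in both arms and the ratio is 1.0 whatever the split. If recording stops but CC detects more events per unit of time, a detection ratio between 1 / 0.944 = 1.06 and 1 / 0.644 = 1.55 would cancel the deficit over the same range.

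**The case against.** A reader might infer that unequal dropout makes collaborative care look safer than it is, as a bias of known direction and size. The SAP does not support that, for four reasons.

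- **Type of dropout.** Trial Progression separates dropout from treatment, from follow-up and from the trial; Sample Size does not say which was unequal. Leaving only the intervention does not end follow-up. If the whole excess were of that kind, there would be no such bias. Against this, the dropout is given as a reason for raising the allowance for loss to follow-up, which suggests that some of it did end follow-up. That is an inference, and its amount is unknown.
- **Capture.** The 26% concerns a postal questionnaire outcome, and an unreturned questionnaire is not a withdrawal. Serious events were identified continuously through a separate route, and deaths were flagged for everyone. For deaths this settles the matter. For hospitalisations and other medically important conditions, no comparable route that reaches every randomised participant is stated, and after full withdrawal Analysis Population ends the data.
- **Detection.** Only collaborative care has 8-10 weekly sessions with symptom monitoring, in an unblinded trial. This could raise recorded events in that arm and push the other way. The point stands, but a possible opposing bias is no reason to leave observation time out.
- **Weight.** The table is descriptive, dropout is reported by type and arm, and counts over all randomised patients are a legitimate description. That limits the harm and is a reason to keep the crude figures, but not to leave them alone.

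**Conclusion.** The point holds in a limited form. The planned summaries ignore time observed in a trial whose SAP reports unequal dropout and ends data at full withdrawal. They may therefore understate non-fatal events in collaborative care wherever dropout ended the recording of events; deaths are not affected.

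Neither the net direction nor the size is established. The effect is nil if recording continued after dropout. If it stopped, the illustration gives an apparent ratio of about 0.64 to 0.94 with equal true rates. That range rests on assumed dropout splits and timings, a constant event rate and no capture after dropout; only the 26% average comes from the SAP. The consequence is confined to the descriptive safety comparison.

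**What to change.** In section 6, Adverse Events:

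- Keep the crude counts, percentages and means, and state that the denominator is all randomised patients.
- Add, by arm, total person-time observed and adverse events per person-year, with a 95% confidence interval that allows for repeat events in the same patient.
- Define person-time as running from randomisation to the earliest of death, recorded withdrawal from follow-up or from the trial, or 12 months. Count in the rate only events dated within it.
- Do not end person-time at withdrawal from the intervention alone, because follow-up continues. Do not end it at last contact either: contact is weekly in collaborative care but scheduled only at 4 and 12 months in usual care, so that rule would itself distort the comparison.
- Note when reporting that the rates do not correct for unequal detection between arms.

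**Cost.** A few lines of SAP text and minor programming. Randomisation dates and status changes are already in the study management database (section 5, Data Sources); the rates also need event dates, assumed to be among the adverse event details held.

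**Limits.** The rates assume a roughly constant event rate and withdrawal unrelated to the risk of an event. Participants who fall silent without a recorded withdrawal would still count as observed to 12 months, so some understatement could remain.

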### **Departures from the Protocol**

Any details specified in the Casper protocol that have been amended in this analysis plan are detailed in Table 2.

Table 2: Departures from Protocol

Protocol Version 2.8 (03/12/ 2013)	Statistical Analysis Plan	Reason for Change
Analyses will be conducted in Stata version 10.	Analyses will be conducted in Stata version 13 or later.	Latest analytical software should be used.
The statistician conducting the analyses will remain blind to treatment group until all data summaries and results are finalised.	The statistician will be kept blind to group allocation until the primary analysis has been completed and checked by the second statistician.	Some of the trial data explicitly reveal treatment allocation, and it would not be feasible to ensure blindness throughout.
A logistic regression model will be used to compare collaborative care with usual care on the primary outcome.	A covariance pattern linear mixed effects model will be used to compare collaborative care with usual care on PHQ-9 scores at 4 months.	Including the word 'logistic' was an error in the protocol, as the primary PHQ-9 outcome is continuous. In order to maximise the use of available data, mixed models will be used instead of individual regressions at each time point.
Appropriate sensitivity analyses will be used to examine the effects of missing data on outcomes.	In order to investigate the impact of missing data, any predictors of non-response will be included as covariates in the primary analysis model only.	As the analysis of secondary outcomes is more exploratory in nature, the sensitivity analysis was restricted to the primary outcome only.
Binary PHQ-9 not mentioned.	Binary PHQ-9 (cut-off: $\geq 10$ score points) at 4 and 12 months will be included as a secondary outcome.	The published protocol paper lists binary description of the PHQ-9 as a secondary outcome and has been omitted in error from the full protocol.
To explore the potential clustering within collaborative care case managers the primary analysis will be repeated adjusting for the clustering using the Huber-White standard estimator (robust standard errors).	The primary analysis will be repeated adjusting for the clustering by case manager by including case managers as a random effect.	As the primary analysis is now a mixed model, a random effect for case managers is appropriate.

Protocol Version 2.8 (03/12/ 2013)	Statistical Analysis Plan	Reason for Change
One of the secondary outcomes: Medication	Medication changed to Mental Health Medication	It was agreed (Casper Data Meeting 25/03/2014) to use only the self-reported questionnaire data in the effectiveness analysis, which refers to mental health medication only. Objective medication data will be analysed as part of the economic analysis.

## 9. Appendices

### CONSORT Diagram
